6.4.9 COVID-19 DISEASE MONITORING

During both the Phase 2 and Phase 3 segments of the trial, all subjects will be monitored for the development of symptoms suggestive of COVID-19 disease. For the Phase 3 segment, frequent (approximately bi-weekly) scheduled clinic visits or phone calls will occur.

All subjects in the trial should be instructed to do the following:

- Take their temperature daily at home starting on the Day 0 visit for the duration of the trial.
- Monitor for symptoms suggestive of COVID-19 (e.g., feeling feverish or chills, cough, shortness of breath or difficulty breathing, fatigue, muscle or body aches, headache, new loss of taste or smell, sore throat, congestion or runny nose, nausea or vomiting, diarrhea) starting on the Day 0 visit for the duration of the trial.

If at any time during the study, the subject experiences a fever of $\geq 100.4^{\circ}F/38^{\circ}C$ or symptoms suggestive of COVID-19, the subject should contact the site. The site staff should arrange for a clinic visit (COVID-19 assessment visit) within 3 days of the site being aware of either a positive SARS-CoV-2 test or COVID-19 symptom onset. The COVID-19 assessment visit may be performed either at the clinic, in the subject's vehicle or in the subject's home.

Subjects with a confirmed COVID-19 diagnosis, per the case definition outlined in Section 3.7, prior to dose 2 or who have a positive SARS-CoV-2 PCR test at Day 0 will be discontinued from further dosing and will be followed until EOS for safety and resolution of COVID-19. If a subject is due for Dose 2 but SARS-CoV-2 RT-PCR results are not yet available from either Day 0 or a Suspected COVID-19 Assessment Visit, they should be dosed on schedule as long as they are currently asymptomatic.

Subjects with virologically confirmed SARS-CoV-2 infection will return for a convalescent visit approximately 28 days after symptom onset, or in the absence of symptoms, after the collection date of any specimen testing positive for SARS-CoV-2 RT-PCR. If symptoms are ongoing at 28 days after symptom onset, the site should follow up with the subject via phone call or unscheduled visit after symptom resolution or stabilization. Recovery from COVID-19 disease requires either resolution of clinical symptoms except for loss of taste/smell, or with sequelae that appear to be permanent.

Subjects who require medical care for COVID-19 (or any other suspected condition) will be referred to their primary health care provider or a medical treatment facility if the Investigator believes that the subject should be managed beyond routine care that can be

INO-4800	COVID19-311
Inovio Pharmaceuticals, Inc.	Clinical Protocol

provided by the study site. Subjects referred for treatment will continue study follow-up according to the protocol schedule. If subjects are treated or hospitalized due to their illness, the study team will request COVID-19 specific test results, treatments, treatment outcomes and diagnostics from medical treatment facilities with the subject's written permission. These results and diagnostics will be recorded in the study and/or safety database consistent with protocol reporting requirements.

6.5 **IMMUNOGENICITY ASSESSMENTS**

Whole blood and serum samples will be obtained at visits specified in the Schedule of Events (Tables 3 and 4) for cellular and humoral immunology assessments. Binding ELISA will be evaluated at serial timepoints. Cellular sampling requires 32 mL of whole blood be collected at each visit. Humoral sampling requires collection of 8.5 mL of whole blood in a single 10-mL red top serum collection tube to produce two serum aliquots of 2 mL each. However, baseline (Day 0) immunology samples are required to serve as a baseline for all subsequent immunology testing. Therefore, a total of 68 mL whole blood for cellular sampling and 8 mL serum for humoral sampling is required on Day 0 prior to 1st dose. Subjects may be asked to return for additional blood draws if collected blood sample is lost or unevaluable for any reason. Details of the immunology sample collection and shipment information will be provided in the Laboratory Manual.

Humoral samples will be collected on all subjects and cellular samples will be collected at selected sites (from approximately 711 subjects). Both humoral and cellular analysis will be conducted in the first 102 subjects age 18-50 and in the first 102 subjects age 51 and older enrolled at the sites that are selected for cellular sample collection. In addition, cellular and humoral samples will be analyzed on all subjects with COVID-19 when samples are available.

The immune responses to INO-4800 will be measured using assays that include a pseudovirus-based neutralization assay and ELISpot. Determination of additional analyses using assays not specified, such as assessment of immunological gene expression or flow cytometry, assessment of immunological protein expression on collected samples for immunological endpoints will be made on an ongoing basis throughout the trial.

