In the Phase 3 segment, approximately 10,002 seronegative and 402 seropositive subjects 18 years of age and older will be randomized at a 2:1 ratio to receive either active investigational product (INO-4800, 2.0 mg) or placebo. See Table 2 and Figure 1. Approximately half of seronegative subjects and approximately half of seropositive subjects will be 18-50 years of age, and the other half will be \geq 51 years of age as is operationally feasible.

Subjects will be randomized in a stratified manner according to (a) age category (18-50 years vs. ≥51 years) on Day 0, and (b) presence or absence on Day 0 of any of the following underlying medical conditions that increase risk of severe COVID-19 disease, per U.S. Center for Disease Control (CDC) criteria [1], as listed below:

[figure not shown]
- Cancer
- Chronic kidney disease
- Chronic lung diseases, including Chronic obstructive pulmonary disease (COPD), asthma (moderate-to-severe), interstitial lung disease, cystic fibrosis, pulmonary hypertension
- Neurologic conditions including stroke or cerebrovascular disease that do not impact cognition
- Diabetes (type 1 or type 2)
- Hypertension
- Heart conditions, such as heart failure, coronary artery disease, or cardiomyopathies
- HIV infection
- Liver disease
- Obesity (BMI \ge 30 kg/m2)
- Sickle cell disease or thalassemia, or
- Smoking (current or former smoker).

Treatment Arm	Sero status	Expected Number of Subjects	Approx. Expected Number of Subjects by Age Group		Dosing Days	Number of Injections + EP per Dosing Visit	INO-4800 (mg) per injection	INO-4800 (mg) per Dosing Visit	Total Dose of INO-4800 (mg)		
		,	18-50	51+					(9)		
INO-4800	Seroneg	6668	3334	3334	0, 28	0.00	0.00	2	1.0	2.0	4.0
INO-4000	Seropos	268	134	134		.0 2	1.0	2.0	4.0		
Disasha	Seroneg	3334	1667	1667	0, 28	2	0	0	0		
Placebo	Seropos	134	67	67							
T . (.)	Seroneg	10002	5001	5001							
Total	Seropos	402	201	201							
Tot	al	10404		•							

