4.2.2 PHASE 3 SEGMENT

- Acute febrile illness with temperature ≥100.4°F (38.0°C) or acute onset of upper or lower respiratory tract symptoms (e.g., cough, shortness of breath, sore throat) within 72 hours prior to Day 0 dosing;
- Positive serologic test for SARS-CoV-2 at Screening (after approximately 402 subjects positive for SARS-CoV-2 serologic test are randomized, this criterion will apply to all remaining subjects);
- c. Pregnant or breastfeeding, or intending to become pregnant or intending to father children starting from the Screening visit until the last dose;
- d. Positive urine pregnancy test during screening or immediately prior to dosing;
- e. Known history of uncontrolled HIV based on a CD4 count less than 200 cells/mm³ or a detectable viral load within 3 months prior to screening;
- f. Is currently participating or has participated in a study with an investigational product within 30 days prior to Day 0 (documented receipt of placebo in a previous trial would be permissible for trial eligibility);
- g. Previous or planned receipt of an investigational (including Emergency Use Authorization (EUA) or local equivalent authorization) or licensed vaccine for prevention or treatment of COVID-19, MERS or SARS (documented receipt of placebo in previous trial would be permissible for trial eligibility);
- h. Immunosuppression as a result of underlying illness or treatment including:
 - Primary immunodeficiencies (conditions including hypothyroidism, Hashimoto's thyroiditis and vitiligo are allowed);
 - Long term use (≥7 days) of oral or parenteral glucocorticoids at a dose of ≥20 mg/day of prednisone equivalent (use of inhaled, topical, nasal, otic, and ophthalmic corticosteroids are allowed) in the past 6 months;
 - Current or anticipated use of disease modifying doses of systemic anti-rheumatic drugs (e.g., azathioprine, cyclophosphamide, cyclosporine, methotrexate) and biologic disease modifying drugs such as TNF-α inhibitors (e.g., infliximab, adalimumab or etanercept) or others;

INO-4800	COVID19-311
Inovio Pharmaceuticals, Inc.	Clinical Protocol

- History of solid organ or bone marrow transplantation;
- History of or current receipt of any other clinically significant immunosuppressive drugs
- Diagnosis of an autoimmune disease that may jeopardize the safety of the subject or require therapy that would interfere with study assessments or endpoint evaluation, or otherwise impact the validity of the study results.

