8.5.2.2 Immunogenicity

Phase 3 Segment

INO-4800	COVID19-311
Inovio Pharmaceuticals, Inc.	Clinical Protocol

Post-baseline increases from baseline in interferon-γ ELISpot response magnitudes will be compared between treatment groups using differences in medians and associated non-parametric 95% CIs.

Post-baseline increases from baseline in neutralizing antibody response titers will be compared between treatment groups using ratios of geometric mean fold-rises and associated t-distribution based 95% CIs.

The summaries listed above will be stratified according to disease status of the subjects and by baseline SARS-CoV-2 serostatus.

Valid samples for statistical analysis purposes will be those collected: at least 6 and no more than 30 days after Dose 2 for the Week 6 timepoint; at least 174 and no more than 198 days after Dose 2 for the Week 30 timepoint; and at least 356 and no more than 380 days after Dose 2 for the Week 56 timepoint. Baseline is defined as the last measurement prior to the first treatment administration.

The PP population will be used for these immunogenicity analyses.

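### The Phase 3 immunogenicity set is chosen by order of enrolment without regard to serostatus, so the number of seronegative subjects behind secondary endpoints 3a and 3b is not controlled

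*Protocol*

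**What the plan says.** All references are to protocol version 7.0.

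- **Selection of the set (Section 6.5).** Humoral and cellular analysis is done "in the first 102 subjects age 18-50 and in the first 102 subjects age 51" or over, counted at those sites picked for cellular collection. Serostatus is not mentioned. On sampling, the section says: "Humoral samples will be collected on all subjects and cellular samples will be collected at selected sites (from approximately 711 subjects"). It also says: "In addition, cellular and humoral samples will be analyzed on all subjects with COVID-19 when samples are available".
- **Entry of seropositives (Section 4.2.2, criterion b).** A positive serologic test at Screening excludes a subject only from a certain point: "after approximately 402 subjects positive for SARS-CoV-2 serologic test are randomized, this criterion will apply to all remaining subjects".
- **Planned mix (Synopsis and Section 3.0).** The Phase 3 segment plans "approximately 10,002 seronegative and 402 seropositive subjects", randomised 2:1. Section 8.7 stratifies randomisation by age category and risk condition, not by serostatus.
- **Analysis.** Section 8.5.2.2 has the secondary ELISpot and neutralising-antibody summaries "stratified according to disease status of the subjects and by baseline SARS-CoV-2 serostatus". The Phase 3 exploratory summaries in Section 8.5.9.2 (ELISA, cellular and neutralising responses) are stratified by disease status only.

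**The concern.** Two rules in the protocol interact. One lets seropositive subjects in until a trial-wide cap is reached and then shuts them out. The other takes the earliest enrollees at certain sites as the immunogenicity set. If the two periods overlap, the set holds more seropositives than the trial as a whole. Nothing reserves places for seronegatives.

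Primary efficacy is assessed in subjects who are seronegative and RT-PCR negative at baseline (Section 8.4). The immune response in that kind of subject is what helps a reader interpret the efficacy result. It carries added weight here because Section 1.3.7 justifies the move to a severe-disease primary endpoint by preserved T cell responses, and endpoint 3a measures T cell response. The selection rule can shrink that stratum, and the placebo third shrinks with it. In the exploratory summaries the two serostatus groups would also be pooled.

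**Working it through.** **The plan's own figure.** 2 x 102 = 204 subjects, which is 136:68 under 2:1 allocation, or 68:34 per age group. The protocol gives no SD, effect size or precision target for 102, so the figure cannot be derived further.

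**When entry becomes front-loaded.** The planned seropositive share is 402/(10,002 + 402) = 402/10,404 = 3.9%. Let s be the seropositive share of entrants while criterion b is open. The cap fills after 402/s randomised subjects, which is before the end of enrolment whenever s exceeds 3.9%.

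**No floor from the cap.** Table 2 plans 201 seropositives per age group, more than the 102 places, so the cap alone does not guarantee any seronegative subject in the set.

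**Size.** The protocol does not state s, so a range is assumed. If all 204 subjects enter while seropositives are admitted, the expected seronegatives are 204(1-s), of whom 68(1-s) are on placebo. With the same SD and arm ratio, the seronegative confidence interval widens by 1/sqrt(1-s) relative to 204 seronegatives.

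| s (assumed) | Cap fills after | Seronegatives of 204 | of whom placebo | CI width ratio |
|---|---|---|---|---|
| 3.9% | 10,404 | 196 | 65 | 1.02 |
| 10% | 4,020 | 184 | 61 | 1.05 |
| 20% | 2,010 | 163 | 54 | 1.12 |
| 30% | 1,340 | 143 | 48 | 1.20 |
| 50% | 804 | 102 | 34 | 1.41 |
| 60% | 670 | 82 | 27 | 1.58 |

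Per-protocol exclusions come on top. The width ratio fits the neutralising-antibody contrast on the log scale most directly. For the difference in medians used for ELISpot it is a large-sample approximation.

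**Dependence on site timing.** The table is conditional on overlap. Suppose instead that the cellular sites enrol in step with the whole trial and have the same seroprevalence. They would then receive about 402 x 711/10,404 = 27 seropositives in all. The set would keep at least 204 - 27 = 177 seronegatives, and the width ratio would be at most sqrt(204/177) = 1.07. If those sites open after the cap is reached, the loss is nil. The larger losses need the cellular sites to enrol early relative to the rest, or to have higher local seroprevalence.

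**Enough stored samples for a fix.** Even at 60% seropositivity throughout, 711 x 0.40 = 284 seronegatives have cellular samples. That is about 142 per age group if ages split evenly, above the 102 needed.

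**The case against.** The strongest case on the other side has five parts.

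1. **Efficacy is untouched.** A reader might infer that seropositives displace seronegative subjects whom the efficacy result needs. The protocol does not support that. Primary efficacy uses all per-protocol subjects who are seronegative and RT-PCR negative at baseline, from 10,002 planned seronegatives, and the 402 seropositives are enrolled in addition. The displacement there is zero. This stands in full.
2. **The size rests on unstated inputs.** Neither early seroprevalence nor the opening dates of the cellular sites is given. At 3.9% the loss is about 8 of 204. This stands, and it is why the result is a range and not a figure.
3. **This is precision, not bias, and no target is missed.** Section 8.5.2.2 reports by serostatus, so the secondary seronegative estimates are not contaminated. Section 8.3 has no formal hypothesis beyond primary efficacy. This stands for the secondary summaries. It does not hold for the exploratory ones, where serostatus is not a stratum.
4. **The objective is not limited to seronegatives.** Secondary objective 3 names no serostatus, unlike objective 2, so including both groups is legitimate. True, but the plan reports them separately without fixing the size of either.
5. **Other immune data exist.** Phase 2 planned about 400 seronegatives, 150 of them at the 2.0 mg dose, and samples from COVID-19 cases are also assayed. Phase 2 supports dose selection, and its data are kept independent of Phase 3. The COVID-19 cases fall under a different disease status and do not refill the stratum.

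**Conclusion.** The concern holds as a defect in the selection rule, of moderate importance at most. As written, the seronegative number behind endpoints 3a and 3b is an accident of early seroprevalence and site timing. If the set fills while seropositive entry is open, it runs from 196 of 204 at a 3.9% seropositive share to 82 at 60%, with intervals 1.02 to 1.58 times as wide. If the cellular sites enrol in step with the trial, the loss is at most about 27 subjects. The figures are expectations: serostatus is not a randomisation stratum, so the 2:1 split among seronegatives holds only on average.

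The consequence is confined to the precision of secondary and exploratory immunogenicity results, plus the pooling of serostatus groups in the exploratory summaries. It would be wrong to conclude that a large loss is certain or that primary efficacy is weakened. This is not a matter left for a separate analysis plan, because Section 6.5 itself fixes the rule.

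**What to change.** - **Section 6.5.** Define the set as the first 102 subjects aged 18-50 and the first 102 aged 51 and older at the cellular sites who meet the same baseline condition as the primary efficacy population: seronegative and RT-PCR negative. Choose them from the stored samples, because the Day 0 RT-PCR result is not required before dosing. Say which serology counts, since Section 6.4.8 uses a Spike rapid test at Screening and a Nucleocapsid assay from Day 0. Selection then uses pre-dose information only, so the randomised comparison is preserved, and the set holds 204 seronegatives (136:68 expected) whatever s is.
- **Seropositive set.** Add a separate set of a fixed, stated size. Assaying every seropositive met while 204 seronegatives accrue would mean 204s/(1-s) subjects: 87, 204 or 306 at 30%, 50% or 60%.
- **Section 8.5.9.2.** Add baseline serostatus to the stratification of the Phase 3 exploratory immunogenicity summaries.

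The cost is a few sentences and extra assays on samples already planned for collection, limited to the stated size of the seropositive set. No additional blood draws are needed.

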7.0 EVALUATION OF SAFETY AND MANAGEMENT OF TOXICITY

7.1 SAFETY PARAMETERS

The safety of INO-4800 will be measured and graded in accordance with the Common Terminology Criteria for Adverse Events (CTCAE), version 5.0.

7.2 ADVERSE EVENTS (AES)

Any untoward medical occurrence in a patient or clinical investigation subject administered a pharmaceutical product and which does not necessarily have a causal relationship with this treatment.

An AE can therefore be any unfavorable and unintended sign (including an abnormal laboratory finding, for example), symptom, or disease temporally associated with the use of a medicinal product, whether or not considered related to the medicinal product.

Adverse Events (AEs) include the following:

• Pre- or post-treatment complications that occur as a result of protocol mandated procedure during or after screening (before the administration of clinical trial drug);

INO-4800	COVID19-311
Inovio Pharmaceuticals, Inc.	Clinical Protocol

- Any pre-existing condition that increases in severity, or changes in nature during or as a consequence of the clinical trial drug administration phase;
- Complications of pregnancy (refer to Section 7.11).

Adverse Events (AEs) do not include the following:

- Medical or surgical procedures (e.g., surgery, endoscopy, tooth extraction, transfusion) performed; however, the condition that leads to the procedure is an AE;
- Pre-existing diseases or conditions or laboratory abnormalities present or detected before the Screening Visit that do not worsen;
- Situations where an untoward medical occurrence has not occurred (e.g., hospitalization for elective surgery, social and/or convenience admissions);
- Overdose without clinical sequelae;
- Any medical condition or clinically significant laboratory abnormality with an onset date before the ICF is signed, is not an AE; it is considered to be pre-existing and will be documented on the medical history CRF;
- Uncomplicated pregnancy;
- An induced elective abortion to terminate a pregnancy without medical reason;
- Confirmed COVID-19 disease.

7.3 Adverse Drug Reaction (ADR)

All noxious and unintended responses to a medicinal product related to any dose. This means that a causal relationship between the medicinal product and an adverse event is at least a reasonable possibility (i.e., the relationship cannot be ruled out).

7.4 SERIOUS ADVERSE EVENTS (SAEs)

An SAE is any untoward medical occurrence that at any dose:

- Results in death;
- Is life-threatening;
 - Refers to an event in which the subject was at risk of death at the time of the event. It does not refer to an event which hypothetically might have caused death if it were more severe
- Requires inpatient hospitalization or prolongation of existing hospitalization;
 - Includes any hospitalization in which the subject has been admitted to the hospital regardless the length of stay, even if the hospitalization is only a precautionary measure to allow continued observation. However, hospitalization (including hospitalization for an elective procedure) for a pre-existing condition that has not worsened, does not constitute an SAE
- Results in persistent or significant disability/incapacity;
 - A substantial disruption of a person's ability to conduct normal life functions (i.e., the adverse event resulted in a significant, persistent or permanent change, impairment, damage or disruption in the subject's body function/structure, physical activities and/or quality of life)
- Results in congenital anomaly or birth defect and/or;
- An important medical event.

INO-4800	COVID19-311
Inovio Pharmaceuticals, Inc.	Clinical Protocol

 An event that may not be immediately life-threatening or result in death or hospitalization but may jeopardize the subject or may require intervention to prevent one of the other outcomes listed above. Examples of such events are intensive treatment in an emergency room or at home for allergic bronchospasm, blood dyscrasias or convulsions that do not result in hospitalization, or development of drug dependency or drug abuse

Clarification of Serious Adverse Events (SAEs)

- Death itself is not an AE. Death is an outcome of an AE, but when the cause of death has not been provided, use the event term: death of unknown cause;
- Confirmed COVID-19 disease that requires hospitalization is recorded on the Suspected COVID-19 Clinical Event CRF, and not recorded as an SAE;
- COVID-19 disease with an outcome of death is recorded on the Suspected COVID-19 Clinical Event CRF, and not recorded as an SAE;
- The subject may not have been receiving an investigational medicinal product at the occurrence of the event;
- Complications associated with COVID-19 disease that occur or prolong hospitalization are recorded on the Suspected COVID-19 Clinical Event CRF;
- The Pregnancy outcomes of spontaneous abortion (miscarriage), ectopic pregnancy, fetal demise/stillbirth in a subject or subject partner following exposure to study treatment is considered to be an SAE.

7.5 **UNEXPECTED ADVERSE DRUG REACTION**

An adverse reaction, the nature or severity of which is not consistent with the applicable product information (e.g., Investigator's Brochure [IB] for an unapproved investigational product, package insert/summary of product characteristics for an approved product).

